5.2.2. Packaging and Labeling

The ODV tablets, CCI [REDACTED], are packaged in white, high-density polyethylene bottles. Each bottle contains 10 tablets and polyester packing material. Each bottle is enclosed with a white, continuous thread, child-resistant polypropylene screw cap with an induction-sealed and aluminum-faced liner.

Study drugs to be distributed to participating centers shall be labeled to meet applicable requirements of the US Food and Drug Administration (FDA), the EU Guideline to Good Manufacturing Practice - Annex 13 (Investigational Medicinal Products), or Annex 6 for CTR, the Japan-GCP (Ministerial Ordinance on GCP for Drugs), as applicable, and/or other local regulations, as applicable.

5.2.3. Storage and Handling

ODV tablets, **CCI** [REDACTED], should be stored below 30 °C (86 °F). Storage conditions are specified on the label. Until dispensed to the participants, all bottles of study drugs should be stored in a securely locked area, accessible only to authorized site personnel.

To ensure the stability and proper identification, study drugs should not be stored in a container other than the container in which they were supplied. Keep the bottle tightly closed to protect from moisture.

Consideration should be given to handling, preparation, and disposal through measures that minimize drug contact with the body. Appropriate precautions should be followed to avoid direct eye contact or exposure when handling.

5.3. Prior and Concomitant Medications

5.3.1. Prior and Concomitant Medications That Are Prohibited or Used With Caution

Medications in [Table 4](#) are prohibited or to be used with caution while participants are taking study drugs. In instances where a prohibited medication is initiated before discussion with the Gilead medical monitor, the investigator must notify Gilead as soon as he/she is aware of the use of the prohibited medication.

There are no restrictions on the symptomatic treatment of COVID-19 other than those indicated in [Table 4](#). There are no restrictions on concomitant medications based on potential for PK DDI with ODV.

Table 4. Prior and Concomitant Medications That Are to Be Used With Caution or That Are Prohibited Because of Impact on Efficacy Assessments or Participant Safety

Medication Class	Medications to Be Used With Caution	Prohibited Medications ^a
COVID-19 medications	—	RDV, molnupiravir, nirmatrelvir/ritonavir, monoclonal antibodies against COVID-19

COVID-19 = coronavirus disease 2019; RDV = remdesivir

a Concomitantly with ODV.

5.4. Dosage and Administration

Participants aged \geq 6 years to $<$ 18 years and weighing \geq 40 kg will receive ODV **CCI** [REDACTED] administered orally BID for 5 days.

Participants aged \geq 6 years to $<$ 18 years and weighing \geq 20 kg to $<$ 40 kg will receive ODV **CCI** [REDACTED] administered orally BID for 5 days.

The doses should be taken approximately 12 hours apart.

Obeldesivir may be administered with or without food.

Participant to withhold their dose prior to arriving to the site on Day 5, as the dose will be administered at the site.

For participants aged < 6 years and weighing < 20 kg, dose will be informed by PK modeling (Section 1.4), and an age appropriate formulation will be developed and additional information will be provided in a protocol amendment.

5.5. Accountability for Study Drugs

The investigator is responsible for ensuring adequate accountability of all used and unused study drug bottles. This includes acknowledgment of receipt of each shipment of study drug (quantity and condition). All used and unused study drug bottles dispensed to participants must be returned to the site.

Each investigational site must keep accountability records that capture:

- The date received, quantity, and condition of study drug bottles
- The date, participant number, and the quantity of study drug bottles dispensed
- The date, quantity of used and unused study drug bottles returned, along with the initials of the person recording the information

5.5.1. Study Drug Return or Disposal

Gilead recommends that used and unused study drugs, which includes bottles, be destroyed at the site. If the site has an appropriate standard operating procedure for drug destruction as determined by Gilead, the site may destroy used (empty or partially empty) and unused study drug bottles in accordance with that site's approved procedural documents. A copy of the site's approved procedural document will be obtained for the electronic trial master file. If the study drug is destroyed at the site, the investigator must maintain accurate records for all study drugs destroyed. Records must show the identification and quantity of each unit destroyed, the method of destruction, and the person who disposed of the study drugs. Upon study completion, copies of the study drug accountability records must be filed at the site. Another copy will be provided to Gilead.

If the site does not have an appropriate standard operating procedure for study drug destruction, used and unused study drugs are to be sent to the designated disposal facility for destruction. The study monitor will provide instructions for return.

The study monitor will review study drug supplies and associated records at periodic intervals.

6. STUDY PROCEDURES

The study procedures to be conducted for each participant screened or enrolled in the study are presented in tabular form in [Table 1](#) and described in the sections below.

The investigator must document any deviation from the protocol procedures and notify Gilead or the contract research organization.

6.1. Informed Consent

Each participant and/or participant's parent or legal guardian must sign an informed consent form (ICF) or assent form, as required by IRB/IEC/local or national requirements, prior to the conduct of any screening procedures.

6.2. Screening, Participant Enrollment, and Treatment Assignment

Participants will be screened within 48 hours before enrollment in the study. Each participant will be assigned a unique screening number using an IRT. Participants meeting all of the inclusion criteria and none of the exclusion criteria will return to the investigational site within 48 hours for enrollment into the study. Screening and enrollment can occur on the same day, where possible.

Entry into screening does not guarantee enrollment into the study. In order to manage the total study enrollment, Gilead, at its sole discretion, may suspend screening and/or enrollment at any site or study wide at any time.

Once written informed consent/assent has been obtained, all screening and admission tests and assessments have been assessed (including recording the date of the latest COVID-19 vaccination shot or booster), and study eligibility has been confirmed, participants will be enrolled to receive ODV on Day 1.

Participants will receive ODV as described in Section [5.4](#).

6.3. Instructions for Study Procedures

An in-person visit will occur either at a medical facility or as a remote visit at home by a health care professional (where permitted).

6.3.1. Adverse Events

From the time informed consent/assent is obtained through the first administration of study drug, record all SAEs, as well as any AEs related to protocol-required procedures, on the AE electronic case report form (eCRF). All other untoward medical occurrences observed during the screening period, including exacerbation or changes in medical history, are to be considered medical history. After study drug administration, report all AEs and SAEs. See Section [7](#) for additional details.

6.3.2. Safety Assessments

Safety will be evaluated throughout the study. Refer to [Table 1](#) for schedule of assessments.

6.3.2.1. Physical Examination

Physical examinations conducted throughout the study during in-person visits will be a complete physical examination or a symptom-driven physical examination, as outlined in [Table 1](#). A physical examination will only be conducted by a qualified health care professional.

A complete physical examination includes source documentation of general appearance and the following body systems: head, neck, and thyroid; eyes, ears, nose, throat, mouth, and tongue; chest (excluding breasts); respiratory; cardiovascular; lymph nodes, abdomen; skin, hair, nails; musculoskeletal; and neurological. Urogenital and reproductive examination should only be completed if clinically indicated.

The complete physical examination conducted at screening will also include the following assessments:

- Review medical history, including the date of first COVID-19 symptoms, overall COVID-19 symptoms, demographics, baseline characteristics, allergies, COVID-19 vaccination, and all other medical history.

6.3.2.2. Vital Signs

Refer to [Table 1](#) for vital signs collection time points. Vital signs will be collected at in-person visits only.

Vital sign measurements include heart rate, temperature, blood pressure (mean arterial pressure if available, systolic and diastolic), respiratory rate, and oxygen saturation.

6.3.2.3. Concomitant Medications

Refer to [Table 1](#) for concomitant medications assessment time points and Section [5.3](#) for more information about concomitant medications.

6.3.2.4. Clinical Laboratory Assessments

Refer to [Table 1](#) for clinical laboratory assessment time points.

Following laboratory assessments will be performed:

- Hematology: Complete blood count (CBC) with differential
- Comprehensive metabolite panel (Chemistry 14): ALT, albumin, alkaline phosphatase, aspartate aminotransferase (AST), total bilirubin (and neonatal bilirubin for participants aged <14 days and participants presenting with jaundice), blood urea nitrogen and creatinine

(include BUN:Cr ratio, and eGFR using bedside Schwarz formula if \geq 1 year of age), ionized calcium, carbon dioxide, chloride, total serum protein, potassium, sodium

- Urinalysis

The smallest possible blood vials, such as microtainer tubes, must be used for participants weighing < 15 kg.

Clinical laboratory assessments at other days may be conducted if required by clinical need or local practice. The results of all clinical laboratory tests that are performed as part of clinical care, even if not required by the protocol, should be reported.

6.3.2.5. Age-Specific Assessments

Refer to [Table 1](#) for timing of the following age-specific assessments:

- Length and head circumference for participants < 28 days of age
- Apgar score assessment for participants < 24 hours of age
- Birth weight for participants < 56 days of age
- GA assessment for participants < 1 year of age
- Tanner stage assessment (Appendix [11.5](#)) for participants ≥ 6 years of age. Date of first menses will be documented.
- Neonatal bilirubin panel for participants < 14 days of age

6.3.2.6. Pregnancy Tests

Urine pregnancy tests will be conducted only for female participants of childbearing potential. Refer to Appendix [11.4](#) for participants of childbearing potential.

6.3.3. Hospitalization Details

Following information will be collected for hospitalized participants:

- hospitalization date
- reason for hospitalization
- discharge date
- discharge outcome

6.3.4. Oxygenation/Oxygen Supplementation

Oxygenation/oxygen supplementation information will be collected for hospitalized participants.

The following information need to be collected:

- Oxygen supplementation:
 - room air (no O₂ supplementation)
 - low-flow O₂ (L/min and %)
 - high-flow O₂ (L/min and %)
 - continuous positive airway pressure/bilevel positive airway pressure (fraction of inspired oxygen [FiO₂] or %)
 - high-frequency oscillating ventilation (FiO₂ or %)
 - mechanical ventilation (FiO₂ or %)
 - extracorporeal membrane oxygenation
- Oxygenation:
 - peripheral oxygen saturation or partial pressure of oxygen

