- m Study drug bottle should be returned by the participant on Day 5, if the participant has already completed both doses of study drug. If the participant has the last dose of study drug remaining by the conclusion of the Day 5 in-person visit, the participant may return the study drug bottle if an in-person visit is conducted on any subsequent visits (including EoS visit). Alternatively, the participant may courier the study drug bottle to the site.
- n To be collected for hospitalized participants. Information to be collected: hospitalization date, reason for hospitalization, discharge date, and discharge outcome.
- o To be collected for hospitalized participants. Refer to Section 6.3.4 for information collection on oxygen supplementation or oxygenation.
- p All participants presenting with multisystem inflammatory syndrome in children (MIS-C; <https://emergency.cdc.gov/han/2020/han00432.asp>) should be monitored and treated as clinically indicated.
- q To be collected for hospitalization participants.

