1.5. Benefit-Risk Assessment for the Study

Obeldesivir has shown to have activity in animal models and shares the same active triphosphate metabolite as the approved COVID-19 treatment drug, RDV.

Obeldesivir has also been evaluated in a Phase 1 (single and ascending dose) study where it was safe and well tolerated. Obeldesivir is currently being evaluated in 2 Phase 3 adult population studies (GS-US-611-6273 and GS-US-611-6549). Enrollment in this study will be initiated following the review of safety data from the first occurring Data Monitoring Committee (DMC) of the adult program:

- Data from the first 200 participants, who completed Day 29 visit or prematurely discontinued from the study, in GS-US-611-6273 have been reviewed by the DMC

OR

- Data from the first 150 participants, who completed Day 29 visit or prematurely discontinued from the study, in GS-US-611-6549 have been reviewed by the DMC.

Obeldesivir has the potential benefit to be the first oral COVID treatment for children, which will facilitate treatment of outpatients as well as inpatients.

Potential risks of a participant's study involvement include unknown AEs, general risks associated with laboratory blood draws, and the associated pain and discomfort of phlebotomy.

Strategies to mitigate these risks include close monitoring of participants' clinical statuses, laboratory values, and AEs. Parameters for discontinuation of the study drug due to AEs will be clearly defined and closely followed.

An infectious disease pandemic may pose additional risks to study drug availability, the study visit schedule, and adherence to protocol-specified safety monitoring or laboratory assessments. Refer to Appendix [11.3](#) for further details on the risks and risk mitigation strategy.

Considering the above, the benefit-risk balance for this study is considered positive.

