2. OBJECTIVES AND ENDPOINTS

Primary Objectives	Primary Endpoints

• To evaluate the plasma PK of ODV in pediatric participants with COVID-19• To evaluate the safety and tolerability of ODV in pediatric participants with COVID-19	
• PK parameters (AUC₀₋₁₂, C_{max}, and C_{trough}) for ODV metabolite, GS-441524• Incidence of treatment-emergent AEs by Day 35• Incidence of treatment-emergent laboratory abnormalities by Day 35
Secondary Objectives	Secondary Endpoints

• To assess the impact of ODV on time to sustained alleviation of targeted COVID-19 symptoms in pediatric participants with COVID-19• To evaluate the antiviral activity of ODV on SARS-CoV-2 nasal swab viral load in pediatric participants with COVID-19• To assess the impact of ODV on the requirement for supplemental oxygen in pediatric participants with COVID-19• To evaluate palatability and acceptability of ODV in pediatric participants with COVID-19• To provide data on the use of medications other than RDV and ODV for treatment of COVID-19 in pediatric participants with COVID-19• To assess the impact of ODV on COVID-19-related hospitalizations or all-cause death in pediatric participants with COVID-19	
• Time to sustained alleviation of targeted COVID-19 symptoms by Day 35• Change from baseline in SARS-CoV-2 nasal swab viral load at Day 5• Proportion of participants who require supplemental oxygen support (low flow oxygen, high flow oxygen, noninvasive ventilation, mechanical ventilation, or extracorporeal membrane oxygenation) by Day 35• Assessment of palatability and acceptability scores of each formulation at Day 5• Proportion of participants with concomitant use of medications other than RDV and ODV for treatment of COVID-19 by Day 35• Proportion of participants with COVID-19-related hospitalization or all-cause death by Day 35

CCI

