8.3. Analysis Conventions

8.3.1. Analysis Sets

8.3.1.1. Efficacy

The primary analysis set for efficacy analyses is defined as the Full Analysis Set (FAS). This will include all participants who (1) are enrolled into the study and (2) have received at least 1 dose of study drug.

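### The oxygen-support endpoint covers every dosed participant, but oxygen data are required only from those in hospital, so the proportion can be understated by an unknown amount

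*Protocol*

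**What the plan says.** Protocol Section 2 (and the Synopsis) sets the objective "To assess the impact of ODV on the requirement for supplemental oxygen in pediatric participants with COVID-19" and pairs it with the endpoint "Proportion of participants who require supplemental oxygen support (low flow oxygen, high flow oxygen, noninvasive ventilation, mechanical ventilation", or extracorporeal membrane oxygenation, by Day 35. Neither is limited to inpatients.

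Section 8.5 analyses efficacy in the Full Analysis Set unless otherwise specified. Section 8.3.1.1 defines that set: "This will include all participants who (1) are enrolled into the study and (2) have received at least 1 dose of study drug". Section 1.5 expects an oral drug "which will facilitate treatment of outpatients as well as inpatients".

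The collection rule is narrower. Section 6.3.4 states "Oxygenation/oxygen supplementation information will be collected for hospitalized participants" and then lists the levels of support, from room air to extracorporeal membrane oxygenation. Footnote o to Table 1 says of the oxygen row: "To be collected for hospitalized participants. Refer to Section 6.3.4 for information collection on oxygen supplementation or oxygenation".

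**The concern.** The endpoint is defined on one population and the data are required from a smaller one. A child who receives low-flow oxygen without being admitted meets the endpoint as worded, yet no procedure asks about that oxygen. The numerator is filled systematically only from admitted children, while the denominator is all dosed children.

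At stake is the meaning of a reported secondary result. A low figure could reflect little oxygen need, or oxygen given where nobody was asked to record it, and a reader of the study report could not tell which. The statistical analysis plan can define the event and the handling of missing values, but it cannot recover information that was never collected.

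**Working it through.** This is mainly a comparison of texts.

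**Step 1. Scope of the endpoint.** Section 2: any participant, any level of support from low flow upward, through Day 35. Sections 8.3.1.1 and 8.5: the denominator is all dosed participants.

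**Step 2. Scope of collection.** Section 6.3.4 and Table 1 footnote o: hospitalized participants. The restriction stands in two places, so it is unlikely to be a slip of wording. Section 9.1.6 confines the eCRF to what the protocol's schedule and procedures require.

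**Step 3. Is there another route into the data?**
- Oxygen saturation is a vital sign (Section 6.3.2.2). It is taken only at in-person visits and does not record whether support was given. Days 21 and 28 are virtual.
- Adverse events are collected until 30 days after the last dose (Section 7.3.2), and concomitant medications are reviewed (Section 6.3.2.3). Oxygen use might be mentioned in either. Neither section asks for it, and nothing ties those records to the endpoint. Section 7.1.1 also says that a procedure is not itself an adverse event.

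So capture outside admission is possible but incidental.

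**Step 4. Scale.** Planned minimum N (Section 4.1): 12 in each of Cohorts 1 to 4 plus 4 in Cohort 5, so 4 × 12 + 4 = 52, which reproduces the stated figure. If an unasked child is counted as not needing oxygen, each missed case lowers the proportion by 1/n:
- overall: 1/52 = 1.9 points
- a cohort of 12: 1/12 = 8.3 points
- a cohort of 4: 1/4 = 25 points

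The protocol gives no rate of oxygen use outside hospital, so the number of missed cases k is an assumption. For k = 0 to 4 of 52, the understatement is k/52 = 0 to 7.7 points. As an illustration, two true cases are 2/52 = 3.8% (exact 95% CI 0.5% to 13.2%). If both occurred without admission and neither surfaced elsewhere, the report would show 0/52 = 0% (CI 0% to 6.8%).

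**The case against.** The best defence is that this is one descriptive secondary endpoint in a single-arm study whose primary endpoints are pharmacokinetics and safety. Section 8.5 plans no formal efficacy testing, so alpha, power and sample size are untouched. That stands, and it limits the weight of the point. A second defence is that children who need oxygen will be admitted. The protocol does not say so; if in-hospital oxygen is what is meant, the endpoint should say that.

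A reader might also infer more than the documents support:
- **That sensitivity outside admission is zero.** Incidental capture through adverse event or concomitant medication records is possible, and the protocol does not define hospitalized, so it is not settled whether an emergency department stay counts. Sensitivity is reduced and unknown.
- **That unasked children are certain to be counted as negative.** No section says so, and Section 8.3.2 says missing values are generally not imputed. If such children were instead dropped as missing, the figure would describe hospitalized participants only, which is also not the stated endpoint.
- **That the endpoint merely repeats the hospitalization endpoint.** The list in Section 6.3.4 includes room air, so an admitted child need not be an oxygen case. The other endpoint counts COVID-19-related admission or death from any cause, while the oxygen list is not tied to COVID-19-related admissions.
- **That children already on oxygen at Day 1 are wrongly counted as outcomes.** Several exclusion criteria in Section 4.3 are redacted, so it cannot be judged whether such children can enter. A baseline rule may also properly sit in the statistical analysis plan.
- **That the 1/n figures measure the bias.** They give the weight of one misclassified child in any binary endpoint of that size.

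**Conclusion.** The mismatch is real and should be corrected. The population of the endpoint is all dosed participants; the population from which oxygen data are required is hospitalized participants. Followed as written, the plan has no systematic way to count oxygen given without admission, and the reported proportion can fall below the true one.

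The direction rests on two assumptions: that some oxygen is given without admission, and that children not asked are counted as not needing it. The amount cannot be computed from the protocol, and the assumed range includes no effect at all. The consequence is confined to the interpretation of a secondary descriptive endpoint.

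**What to change.** Choose one of two changes so that Section 2, Section 6.3.4 and Table 1 footnote o agree.

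1. **Widen the collection (keeps the stated objective).** In Section 6.3.4 and footnote o, have all participants or their caregivers asked, at each contact already scheduled through Day 35 and including the virtual Days 21 and 28, whether supplemental oxygen was used since the last contact and at what highest level. Keep flow, FiO2 and saturation detail for hospitalized participants.
2. **Narrow the endpoint.** If only in-hospital oxygen is intended, restate the endpoint in the Synopsis and Section 2 as supplemental oxygen support during hospitalization, and word the objective to match.

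The first option costs a small eCRF addition, repeated at existing contacts, with no new visit, sample or procedure. The second costs only wording, but gives up any statement about oxygen need outside hospital. Both concern data collection and endpoint wording only and leave clinical care unchanged.
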